5.3.3.3 Time to First Achievement of PASI-50

As the PASI score is only collected at each study visit, the time to first occurrence of PASI-50 should be considered as interval-censored data. It is only known that the participant achieved PASI-50 at some point at or before the assessment at which it was first observed and after the previous assessment.

For participants who meet the criteria for PASI-50, the interval start and stop day for first achievement of PASI-50 will be defined as:

Interval start day = Study day of last PASI assessment before PASI-50 was first achieved +1

Interval end day = Study day of PASI assessment at which PASI-50 was first achieved

Participants who do not meet the criteria for PASI-50 during the Part A of the study will be right-censored at the last PASI assessment within 4 days of treatment discontinuation (for participants who did not complete the 16-week treatment period) or the last PASI assessment in Part A (for participants who did complete the 16-week treatment period). For the purposes of the analysis data set, the interval start and stop dates will be defined as:

Interval start day = Study day of last PASI assessment+1

Interval end day = missing

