Psoriasis is a chronic immune-mediated type 1/3 inflammatory skin disease in which hyperactive T cells trigger excessive keratinocyte proliferation. This results in the formation of raised erythematous plaques with scaling. Psoriatic lesions can appear anywhere on the body but are most often seen on the knees, elbows, scalp, and lumbar area. Critical events in the inflammatory process include activation of Langerhans cells and T cells, selective trafficking of activated T cells to the skin, and induction of an inflammatory cytokine and chemokine cascade in skin lesions. Clinical data have validated the role of anti-TNF α , anti-IL-17, and anti-IL-23 therapy in moderate to severe psoriasis. For patients with mild to moderate psoriasis, therapy usually involves topical agents (topical corticosteroids, vitamin D3 analogs), with topical corticosteroids providing the greatest range of efficacy and a wide range of formulations. More recently, physicians are prescribing apremilast, a first-in-class oral PDE4 inhibitor, ahead of biological therapy, which includes etanercept, infliximab, adalimumab, ustekinumab, and secukinumab.

In Evelo study EDP1815-101, a total of 56 participants have participated in Cohorts 1-4, with 36 of these participants receiving EDP1815 once daily; 16 of these were treated for 14 days (healthy volunteers) and 20 participants with psoriasis were treated for 28 days. Clinical responses, similar to apremilast and tofacitinib at the same time point, have been observed on the (psoriatic) LSS and PASI at Day 28. Furthermore, at the Day 42 follow-up visit, when participants were “off treatment” for 14 days, there was continued improvement in the pharmacodynamic response as measured by both LSS and PASI for participants administered the higher dose, but not the lower dose, suggesting a dose relationship on the durability of effect. The safety profile of EDP1815 was similar to placebo, with no SAEs or AEs of severe intensity.

Evelo Biosciences Inc.

EDP1815

Protocol: EDP1815-201 Version 5.0 (Amendment 4)

17 November 2020

The evidence available so far suggests EDP1815 is very well tolerated and it continues to undergo clinical development in mild to moderate psoriasis. A well-tolerated oral therapy could offer significant benefit in the treatment of psoriasis and it is presently anticipated that EDP1815 would be used in established but early disease, before the use of biologic therapies.

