3.1 Study Design

This is a multicenter, randomized, double-blind, placebo-controlled, parallel-cohort, dose-ranging study of participants with mild to moderate plaque psoriasis (Section 4.1).

Part A of the study comprises a screening period of up to 4 weeks, a baseline visit, a treatment period of 16 weeks (8 planned study site visits), and a follow-up visit at Week 20 (4 weeks after cessation of dosing). Part A of the study therefore comprises a total of 11 scheduled study visits, and on completion of Part A, the primary analysis will be performed.

Part B of the study is designed to assess the durability of treatment response and incidence of rebound of psoriasis following cessation of dosing. All participants will attend for skin assessments at Weeks 24 and 28, unless they have previously experienced treatment failure and/or had rebound of disease. A final visit at Week 40 will also be performed for those participants who experienced treatment response at Week 16 of treatment, but have not yet met the definition of disease relapse. Part B of the study therefore comprises a maximum of 3 additional scheduled study visits with a follow-up of up to 40 weeks (24 weeks after cessation of dosing), and on completion of Part B, the final analysis will be performed.

The study design is presented in Figure 3-1, and the SoA is presented in Table 6-1 for Part A, and in Table 6-2 for Part B.

After eligibility is confirmed during the screening period (Section 4.1), participants will be randomly assigned in a 1:1:1 ratio to 1 of the following 3 parallel cohorts:

- Cohort 1: 0.8×10^{11} cells of EDP1815 or matching placebo administered as 1 PIC, once daily (Section 5.2).
- Cohort 2: 3.2×10^{11} cells of EDP1815 or matching placebo administered as 4 PICs, once daily (Section 5.2).
- Cohort 3: 8.0×10^{11} cells of EDP1815 or matching placebo administered as 10 PICs, once daily (Section 5.2).

In each cohort, approximately 75 participants will be randomly assigned in a 2:1 ratio to receive either EDP1815 or matching placebo once daily for 16 weeks.

[figure not shown]
An interim analysis may be performed after at least 50% of participants have completed at least 12 weeks of treatment (Section 7.6.7).

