7.1.2 Secondary Efficacy Estimands

Estimands for the analyses of all secondary endpoints are shown in Table 7-1.

Table 7-1 **Summary of Secondary Estimands**

Population of interest	Endpoint	Consideration of intercurrent events	Summary measure
mITT set	Mean percentage change from baseline in PASI Score at Weeks 4, 8, and 12	To include all data collected prior to treatment discontinuation, regardless of protocol deviations	Posterior mean difference between each active treatment group and pooled placebo at each visit
mITT set	Mean absolute change from baseline in PASI Score at Weeks 4, 8, 12, and 16	To include all data collected prior to treatment discontinuation, regardless of protocol deviations	Posterior mean difference between each active treatment group and pooled placebo at each visit
mITT set	Achievement of PASI-50 at Weeks 4, 8, 12, and 16	To include all data collected prior to treatment discontinuation, regardless of protocol deviations	Posterior odds ratio for response between each active treatment group and pooled placebo at each visit
mITT set	Time to first achievement of PASI-50	To include all data collected prior to treatment discontinuation, regardless of protocol deviations	Hazard ratio for each active group versus placebo
mITT set	Achievement of PASI-75, PASI-90 and PASI-100 at Week 16	To include all data collected prior to treatment discontinuation, regardless of protocol deviations	Proportion of response for each endpoint in each treatment group at each visit
mITT set	Achievement of PGA of 0 or 1 with a ≥ 2 -point improvement from baseline at Week 16	To include all data collected prior to treatment discontinuation, regardless of protocol deviations	Posterior odds ratio for response between each active treatment group and pooled placebo
mITT set	Achievement of PGA of 0 at Week 16	To include all data collected prior to treatment discontinuation, regardless of protocol deviations	Posterior odds ratio for response between each active treatment group and pooled placebo
mITT set	Mean percentage change from baseline in PGA \times BSA at Weeks 4, 8, 12, and 16	To include all data collected prior to treatment discontinuation, regardless of protocol deviations	Posterior mean difference between each active treatment group and pooled placebo at each visit

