5.1 General Study Design and Plan

This is a multicentre, randomised double-blind, placebo-controlled, parallel cohort dose ranging study of participants with mild to moderate plaque psoriasis.

After eligibility is confirmed during the screening period ([Protocol Section 4.1](#)), participants will be randomly assigned in a 1:1:1 ratio to 1 of the following 3 parallel cohorts:

- Cohort 1: 0.8×10^{11} cells of EDP1815 or matching placebo administered as 1 PIC, once daily.
- Cohort 2: 3.2×10^{11} cells of EDP1815 or matching placebo administered as 4 PICs, once daily.
- Cohort 3: 8.0×10^{11} cells of EDP1815 or matching placebo administered as 10 PICs, once daily.

[figure not shown]
In each cohort, approximately 75 participants will be randomly assigned in a 2:1 ratio to receive either EDP1815 or matching placebo once daily for 16 weeks.

As shown in Figure 1, Part A of the study comprises a screening period of up to 4 weeks, a baseline visit, a treatment period of 16 weeks, and a follow-up visit at Week 20, making 11 scheduled study visits in total. On completion of Part A, the primary analysis will be performed.

Part B of the study is designed to assess the durability of treatment response and incidence of rebound of psoriasis following cessation of dosing. All participants will attend for skin assessments at Weeks 24 and 28, unless they have previously experienced treatment failure and/or had rebound of disease. A final visit at Week 40 will also be performed for those participants who experienced treatment response at Week 16 but have not yet met the definition of complete relapse. Part B therefore comprises a maximum of 3 additional scheduled study visits with a follow-up of up to 40 weeks (24 weeks after cessation of dosing). On completion of Part B, the final analysis will be performed.

‘Treatment failure’ is synonymous with ‘starting a new psoriasis treatment’ which is an oral agent, biological, or intermediate or high-potency dose topical therapy for plaque psoriasis. Starting topical unmedicated emollients and low-potency topical steroids which were not taken at baseline does not count as starting a new psoriasis treatment.

Figure 1 Study Schema

Note: PIC=Powder in capsule (formulation). All dosing is once daily.

Note: Since this figure was produced for the protocol, the Interim Analysis has been moved from Week 12 to when the last participant has received their last dose (Week 16).

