5.3.4.2 Treatment-Emergent Adverse Events

An adverse event (AE) will be classified as ‘treatment-emergent’ if the onset date/time was on or after the start date/time of study treatment. Where dates or times are missing or partially missing, AEs will be assumed to be treatment-emergent, unless there is clear evidence (through comparison of partial dates/times, see [Section 7.3.1](#)) to suggest that the AE started prior to dosing.

AEs will be classified into the following study phases based on the onset date/time of the AE after any imputations:

- Pre-Treatment Phase: All AEs with onset date/time prior to the first dose of randomized study treatment
- Treatment Phase: All AEs with onset date/time at the time of or after the first dose of randomized study treatment (Day 1) up to and including the date of the last dose of treatment received.
- Follow-up Phase: All AEs with onset date after the date of the last dose of treatment received.

For participants who complete 16 weeks of dosing per protocol the Treatment Phase will be from Day 1 to Day 112 and the Follow-up Phase will be from Day 113 until their last day in the study. In all cases the day will be assumed to start at 00:00 hours and end at 23:59 hours. Adverse events occurring in both the Treatment Phase and Follow-up Phase are classified as treatment emergent.

For the primary analysis which considers only data collected in Part A, only events which start on or prior to the end of Part A date will be included in the adverse event summaries.

The onset phase of all AEs will be included in the relevant data listings.

For the final analysis, only treatment related events which start in Part B will be included in the adverse event summaries.

Only treatment related events which start in Part B and any Part A AEs which change in Part B will be included in the relevant data listings.

6 Sample Size

The sample size of 225 participants in total, has been chosen to explore the tolerability and safety of EDP1815. Although the study will use a model-based probability inference approach in a Bayesian framework, the following power calculation was also performed (using a basic frequentist approach) in order to give confidence that enough participants are available to find a clinically meaningful difference between active dose and placebo if the below assumptions are met.

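### Time to first PASI-50 counts completers' first responses at Week 20, about four weeks off drug, although its estimand is limited to data before treatment discontinuation

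*SAP*

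**What the plan says.** SAP Section 5.3.3.3 sets the event window and the censoring together. Its censoring rule reads "Participants who do not meet the criteria for PASI-50 during the Part A of the study will be right-censored", so a first PASI-50 at any Part A visit is an event. Participants without one are censored at "the last PASI assessment within 4 days of treatment discontinuation (for participants who did not complete the 16-week treatment period" or at "the last PASI assessment in Part A (for participants who did complete the 16-week treatment period".

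Part A consists of screening, baseline, "a treatment period of 16 weeks, and a follow-up visit at Week 20, making 11 scheduled study visits in total" (SAP Section 5.1). Protocol Section 3.1 describes the last of these as "a follow-up visit at Week 20 (4 weeks after cessation of dosing". Protocol Table 6-1 schedules PASI at that visit.

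For time to first PASI-50, Protocol Table 7-1 says of intercurrent events: "To include all data collected prior to treatment discontinuation, regardless of protocol deviations". SAP Section 9.5 applies the primary estimand approach to the secondary endpoints except partial relapse, relapse and rebound. In SAP Table 3 that approach is while on treatment. PASI more than 4 days after discontinuation is missing up to Week 16, and a footnote extends this to completers whose Week 16 visit falls more than 4 days after the end of treatment. The same table sets Week 20 PASI to missing only for those who did not complete treatment to Week 16.

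SAP Section 9.5.5 reports the survival curves, a generalised log-rank test and the proportion reaching PASI-50 at least once during the study.

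**The concern.** Completers stay at risk, and can have an event, for about four weeks after dosing ends. Early stoppers leave the analysis within 4 days of stopping. The endpoint therefore mixes on-drug and off-drug first responses, while the protocol estimand describes response before discontinuation.

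Whether the extra events are balanced across arms cannot be assumed. Protocol Section 1 reports for the Phase 1 study that 14 days after dosing "there was continued improvement in the pharmacodynamic response as measured by both LSS and PASI for participants administered the higher dose", but not for those on the lower dose. In a dose-ranging trial, the tail of the curves, the log-rank p-value and the ever-responded proportion could reflect persistence after dosing as well as onset of response during it.

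**Working it through.** **1. Time off drug at Week 20.** Inputs: Week 16 visit Day 113 with window 110-116, and Week 20 visit Day 141 with window 141-148 (Protocol Table 6-1). For the last dose, SAP Section 5.3.4.2 states: "For participants who complete 16 weeks of dosing per protocol the Treatment Phase will be from Day 1 to Day 112".
- Week 16 to Week 20: (141 − 113)/7 = 4.0 weeks, which reproduces the protocol's figure.
- Days after last dose: 141 − 112 = 29 to 148 − 112 = 36.
- Days beyond the SAP's 4-day allowance: 29 − 4 = 25 to 36 − 4 = 32.
- Latest in-window Week 16 visit: 116 − 112 = 4 days, so the allowance covers the Week 16 window but not Week 20.

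**2. Does discontinuation include the planned end of dosing?** In Protocol Table 7-1, the relapse rows (Week 16 responders, Weeks 20 to 40) are said to use data collected after treatment discontinuation. There the term must cover completers. The SAP Table 3 footnote also applies the 4-day rule to completers. A completer's Week 16 PASI taken 5 days after last dose would be missing, yet a first response 29 or more days after last dose would count.

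**3. What changes for one participant.** A completer first at PASI-50 at Week 20, with a Week 16 assessment on Day 113, is now an event in the interval Day 114 to Day 141. With a Week 16 cut-off, the same participant is right-censored with interval start Day 114.

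**4. How many participants.** The documents give no figure. SAP Section 6 expects at least 42 participants per active dose and 3 × 21 = 63 on pooled placebo with data through Week 16. For an assumed share first responding at Week 20:

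| Share | Active (n = 42) | Pooled placebo (n = 63) |
|---|---|---|
| 0% | 0 | 0 |
| 2% | 0.8 | 1.3 |
| 5% | 2.1 | 3.2 |
| 10% | 4.2 | 6.3 |

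A simulation shows which shares are plausible. Its assumptions are Week 16 mean changes of −15, −30 and −40, SD 25 and visit correlation 0.85; only the SD matches a planning value in the documents. By Week 16, 9.5%, 25% and 40% reach PASI-50. With no drift after dosing, a further 3.0%, about 5.5% and 6.5 to 7% first do so at Week 20. In relative terms (taking 6.5 for the last) that is 3.0/9.5 = 32%, 5.5/25 = 22% and 6.5/40 = 16% more events. With correlation 0.95 and no drift the increase is about 10 to 22%. With 5 points of worsening off drug it is roughly 2 to 18%.

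**5. Direction.** Assume 20% (placebo) and 30% (active) respond through Week 16, a difference of 10 points:
- adding 0% and 10% at Week 20 gives 40 − 20 = 20 points;
- adding 5% and 5% gives 35 − 25 = 10 points;
- adding 10% and 0% gives 30 − 30 = 0 points.

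The scale matters too. Take the no-drift simulation, −40 against −15:
- Risk difference: 40 − 9.5 = 30.5 points through Week 16, and 46.5 − 12.5 = 34.0 through Week 20.
- Cumulative-hazard ratio: ln(1 − 0.40)/ln(1 − 0.095) = 5.1 through Week 16, and ln(1 − 0.465)/ln(1 − 0.125) = 4.7 through Week 20.

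The same extra events widen one contrast and shrink the other.

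**The case against.** The best defence is that the SAP says what it is doing. Table 3 removes Week 20 PASI only for non-completers, and Section 5.3.3.3 agrees with it. Week 20 is also a visit level in the primary MMRM and in the PASI-50 model. Protocol Section 4.2 defines only early discontinuation, as stopping before the Week 16 visit, so a completer could be said never to have discontinued. Protocol Section 7.6.2 itself reports PASI-50 at least once during the study, without an on-treatment limit.

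Much of this stands. Section 5.3.3.3 does not conflict with the Week 20 sentence of Table 3, and treating completers and early stoppers differently follows from that sentence. The conflict is with Protocol Table 7-1, with the while-on-treatment label and with the 4-day rule as applied to completers. Retaining Week 20 does little harm in a visit-based model, because Week 20 is reported as its own visit. A time-to-first-event endpoint has no fixed visit, so the off-drug response enters the result directly.

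The reach is also limited. Both codings of a Week 20 first responder say that PASI-50 had not been reached by the Week 16 assessment, so the estimated curve through Week 16 should be essentially unchanged.

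From the Phase 1 observation, a reader might infer that the rule favours the high dose. The documents do not support that. They report continued mean improvement over 14 days off drug, not new PASI-50 responses at four weeks. The simulation gives every scenario the same drift, so it does not test a dose-dependent effect.

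**Conclusion.** The point holds as a mismatch between estimand and derivation. As written, the rule counts first responses 29 to 36 days after the last dose in an endpoint that Protocol Table 7-1 limits to data before discontinuation, and SAP Table 8 does not declare the extension. The reading rests on discontinuation including the planned end of dosing, which Table 7-1's own relapse rows and the SAP Table 3 footnote support.

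The size is uncertain. The 3 to 7% of participants depends on assumed means, correlation and no drift, and the treatment contrast can move either way. A claim of systematic bias towards any dose would go beyond the documents.

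The consequence is confined to the tail of the survival curves, the generalised log-rank test and the ever-PASI-50 proportion. Protocol Section 7.6.2 treats secondary p-values as descriptive. The primary endpoint and PASI-50 at Week 16 are unaffected. The change is worth making before unblinding because it is cheap; it is not critical.

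**What to change.** In SAP Section 5.3.3.3, for completers, end both the event window and the censoring at the last PASI assessment through Week 16 that lies within 4 days of last dose. A first response at Week 20 is then right-censored. Both parts must change. If only the censoring date moved, Week 20 responders would remain events while Week 20 non-responders left the risk set at Week 16, which is worse than the present rule. Limit the proportion in SAP Section 9.5.5 to the same window, and show first responses at Week 20 descriptively by arm.

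If the sponsor wants Week 20 included, state that in the estimand for this endpoint, list it in SAP Table 8 as a change from the protocol, and present the through-Week-16 version alongside.

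The cost is a few SAP sentences and somewhat fewer events: about 2 per active dose and 3 on pooled placebo if 5% first respond at Week 20.

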5.3.3.4 Duration Endpoints

The following duration endpoints will be defined:

Duration of remission is defined as time from first achievement of PASI-100 to loss of PASI-100 or start of a new psoriasis treatment whichever occurs first.

Duration of treatment success is defined as time from first achievement of PASI-50 to loss of PASI-50 or start of a new psoriasis treatment whichever occurs first.

Duration of therapeutic effect is defined as time from cessation of study treatment until increase of PASI to 50% of maximum improvement from baseline or start of a new psoriasis treatment whichever occurs first. Maximum improvement from baseline is a participant's lowest post-baseline PASI score. Increase of PASI to 50% of maximum improvement from baseline can only occur at a visit after the visit where maximum improvement from baseline occurred. Any participant who showed no improvement in PASI score from baseline up to end of treatment will not have duration of therapeutic effect calculated. Any participant who showed an improvement prior to end of treatment and whose end of treatment PASI score had already gone above 50% of maximum improvement from baseline will have duration of therapeutic effect equal to zero.

As the PASI score is only collected at each study visit, the duration endpoints should be considered as interval-censored data. Although an exact date of start of new psoriasis treatment will be collected, it is only known that the participant achieved and lost PASI-100/50 status, or achieved an increase of PASI to 50% of maximum improvement from baseline, at some point at or before the assessment at which it was first observed and after the previous assessment.

Duration should be calculated as:

Duration = End Day - Start Day

For duration of remission and duration of treatment success:

Start Day = Study day of PASI assessment at which PASI-100 or PASI-50, respectively, was first achieved

End Day = Study day of PASI assessment at which PASI-100 or PASI-50, respectively, was first lost, or start of new psoriasis treatment whichever occurs first

For duration of therapeutic effect, duration should be calculated as:

Start Day = Study day of end of study treatment

End Day = Study day of PASI assessment at which increase of PASI to 50% of maximum improvement from baseline first occurred, or start of new psoriasis treatment, whichever occurs first

If a participant does not meet the Start Day criteria relevant to a particular duration endpoint at any time during the study the endpoint will not be calculated.

If a participant has not met the End Day criteria relevant to a particular duration endpoint by the final study visit the last PASI assessment in Part A or Part B will be used as the End Day in the calculations above.

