4.1.1 Inclusion Criteria

Each participant must meet all the following criteria to be enrolled in this study:

1. Give written informed consent (signed and dated) and any authorizations required by local law and be able to comply with all study requirements.
2. Males or females ≥ 18 and ≤ 70 years old at the time of informed consent.
3. A documented diagnosis of plaque psoriasis for ≥ 6 months.

4. Have mild to moderate plaque psoriasis with plaque covering BSA of $\geq 3\%$ and $\leq 10\%$ and meet **both** of the following additional criteria:
 - a. PASI score of ≥ 6 and ≤ 15 , and
 - b. PGA score of 2 or 3.

All parameters in this criterion should be reconfirmed at baseline visit prior to randomization.

5. Meet the following contraception criteria:

- a. Male participants:
 - i. A male participant must agree to use contraception as detailed in Appendix 13.1 of this protocol during their participation in this study and for a period of 90 days after the last dose and refrain from donating sperm during this period.
- b. Female participants:
 - i. A female participant is eligible to participate if she is not pregnant (Appendix 13.1), not breastfeeding, and at least 1 of the following conditions applies:
 1. Not a WOCBP as defined in Appendix 13.1, OR
 2. A WOCBP who agrees to follow the contraceptive guidance in Appendix 13.1 during their participation in this study, 28 days prior to the first dose and for at least 1 complete menstrual cycle (≥ 28 days) after the last dose.

6. Agrees to not increase their usual sun exposure during the study.

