6.1 Efficacy Assessments

6.1.1 Psoriasis Area and Severity Index Score

The PASI score will be assessed as described by Langley and Ellis (2004). The PASI is a physician assessment that combines the assessment of the severity of and area affected by psoriasis into a single score in the range 0 (no disease) to 72 (maximal disease). The absolute PASI score in this study is used as part of inclusion criterion #4. The PASI percentage response rates are efficacy endpoints (ie, PASI-50, PASI-75, PASI-90, and PASI-100). For example, the percentage of participants who achieve a 75% or greater reduction in PASI score from baseline is represented by the PASI-75 value. Details of the PASI assessment will be provided in the relevant training material.

Response Definitions based on PASI score at Week 16:

- **Responders:** Participants on treatment achieving PASI-50 or greater at Week 16 visit
- **Relapse:** Increase in PASI score to baseline value or greater, or participant begins a new treatment for psoriasis
- **Partial Relapse:** Loss of PASI-50 response after cessation of study treatment
- **Rebound:** Increase in PASI score to 125% of baseline value or above, or onset of new pustular/erythrodermic psoriasis within 3 months of cessation of study treatment
- **Duration of remission:** Time from first achievement of PASI-100 to loss of PASI-100
- **Duration of treatment success:** Time from first achievement of PASI-50 to loss of PASI-50
- **Duration of therapeutic effect:** Time from cessation of study treatment until increase of PASI to 50% of maximum improvement from baseline

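### SAP 5.3.3.4 defines maximum improvement as a PASI level, so the duration of therapeutic effect records visit timing and not loss of effect

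*SAP*

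**What the plan says.** Protocol 6.1.1 defines the duration of therapeutic effect as "Time from cessation of study treatment until increase of PASI to 50% of maximum improvement from baseline". It gives no formula for maximum improvement.

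SAP 5.3.3.4 keeps the wording and adds a second way to end the period: "time from cessation of study treatment until increase of PASI to 50% of maximum improvement from baseline or start of a new psoriasis treatment". It then supplies the missing definition: "Maximum improvement from baseline is a participant's lowest post-baseline PASI score". Three further rules follow in the same paragraph:

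- Visit-after rule: "Increase of PASI to 50% of maximum improvement from baseline can only occur at a visit after the visit where maximum improvement from baseline occurred".
- Exclusion of non-improvers: "Any participant who showed no improvement in PASI score from baseline up to end of treatment will not have duration of therapeutic effect calculated".
- Zero rule, for an improver "whose end of treatment PASI score had already gone above 50% of maximum improvement from baseline will have duration of therapeutic effect equal to zero".

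The endpoint is exploratory (SAP 4.2), is summarised descriptively (SAP 9.6.1), and has one table, 14.4.2.21 (SAP 15.5.1). SAP Table 8, which lists changes from the protocol, has no entry for it.

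**The concern.** An improvement from baseline is a difference, and SAP 5.3.1.3 itself defines change from baseline as one. The lowest PASI is a level. If the level is put where the difference belongs, the threshold for losing the effect lies below the best score the participant ever reached. Every later score then counts as a loss, including one that has not moved.

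Duration of therapeutic effect is part of a named exploratory objective (Protocol 2.3, SAP 4.1), and Part B exists to assess durability. It is also the only duration endpoint open to any improver; the other two require PASI-50 or PASI-100. Protocol 3.1.1 reports that in Phase 1 the higher-dose group went on improving after dosing stopped. This endpoint should be able to show that pattern, and as written it cannot.

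**Working it through.** **Inputs.** B is baseline PASI, from 6 to 15 by inclusion criterion 4 ("PASI score of ≥ 6 and ≤ 15"). L is the lowest post-baseline PASI. PASI is scored at Weeks 1, 2, 4, 8, 12, 16 and 20 in Part A, and at Weeks 24, 28 and 40 in Part B. The plan gives no figure of its own to reproduce here.

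**Threshold as written.** T = 0.5 × L. If L > 0, then 0.5 × L < L, and no post-baseline score is below L. Every post-baseline score is therefore above T. This is algebra and needs no assumption. If L = 0, then T = 0, and a participant who stays clear already sits on the threshold.

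**Threshold for losing half the improvement.** B − 0.5 × (B − L) = (B + L)/2.

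| B | L | As written, 0.5 × L | Loss of half, (B + L)/2 |
|---|---|---|---|
| 10 | 4 | 2 | 7 |
| 6 | 3 | 1.5 | 4.5 |
| 15 | 5 | 2.5 | 10 |

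**What the rules then produce, for B = 10 and L = 4.**

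- *Lowest score first reached at Week 12, PASI 4 at end of treatment.* Taking the first visit at 4 as the visit of best response (the SAP does not address ties), Week 16 is a later visit and 4 > 2. The zero rule gives duration 0, although no improvement has been lost.
- *Lowest score first reached at Week 16.* The visit-after rule bars an event at Week 16. The next visit is Week 20. If PASI is still 4, then 4 > 2 and the event is recorded there. With the last dose on Day 112 (SAP 5.3.4.2) and Week 20 on Day 141 (Protocol Table 6-1), the duration is 141 − 112 = 29 days, with no worsening.
- *Lowest score at Week 20, after continued improvement off treatment.* If post-treatment scores count towards L, the event falls at Week 24 (Day 169): 169 − 112 = 57 days, again whether or not PASI rose.

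Under the (B + L)/2 threshold, none of these participants has an event until PASI reaches 7.

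**How often each outcome occurs.** This depends on PASI trajectories that the documents do not give, so it was explored by simulation under stated assumptions: 36 scenarios of 100,000 paths each. The SD of percent change was 25% (SAP Section 6). Assumed inputs were a mean Week 16 change of −20% or −40%; a between-subject variance share of 0.5 to 0.95; a linear response or a plateau at Week 8; and a response that wanes, holds or briefly continues off treatment.

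| Quantity | Range over scenarios |
|---|---|
| Improvers given zero, zero rule applied alone | 99–100% |
| Improvers given zero, both rules, lowest score on treatment only | about 20–76% |
| Improvers given zero, both rules, lowest score at any post-baseline visit | about 7–67% |
| Event at Week 20, among those with a non-zero lowest score first reached at Week 16 | 91–100% |
| Improvers given zero under the (B + L)/2 threshold | about 7–45% |

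The fourth row can fall short of 100% because, with an on-treatment lowest score, PASI at Week 20 can in principle drop below half of it.

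**The case against.** The best defence is that the sentence only identifies the visit of best response. The surrounding text speaks of improvement from baseline, refers to the visit at which it was greatest, and treats a zero duration as a special case. All of that fits loss of half the improvement, and a careful programmer might implement it so. As a guide to intent this stands. It does not supply a threshold. For B = 10 and L = 4, half of the maximum improvement could mean PASI 3 (half of the difference of 6, taken as a score) or PASI 7 (half of the improvement lost). Protocol 6.1.1 does not settle which, and Table 8 is silent. The protocol does not share the SAP's error, since it never equates improvement with the lowest score, but it does not repair it either.

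A reader might also infer that almost every duration becomes zero. The documents do not support that. It follows only if the zero rule is applied on its own, and the same paragraph contains the visit-after rule. Read together, a participant whose lowest score is first reached at end of treatment gets the time to the next PASI visit instead. That value is not zero, but it is just as uninformative.

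The scope is also narrow. Relapse, partial relapse and rebound, which serve the secondary Part B objective, do not use this threshold. Nor do the durations of remission and treatment success.

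**Conclusion.** The definition is wrong as written. That the threshold lies below every observed post-baseline score when the lowest score is above 0 rests on algebra alone. The consequence is that durations collapse to zero or to the first PASI visit after the lowest score. They are zero if the zero rule is applied alone, or if the lowest score came before end of treatment. The split between the two outcomes depends on how the rules are combined and on assumed trajectories; the simulated shares show a range and are not a forecast.

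The impact is limited to one exploratory, descriptive endpoint. No primary, secondary or safety result changes. The correction is still worth making now: SAP 5.2 unblinds the data at the end of Part A, and a threshold repaired after that would be chosen with treatment results known.

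**What to change.** Amend SAP 5.3.3.4 before the end-of-Part-A unblinding:

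1. Define maximum improvement as baseline PASI minus lowest post-baseline PASI.
2. Define the event as the first later visit with PASI at or above baseline − 0.5 × maximum improvement, which equals (baseline + lowest)/2. Keep the start of a new psoriasis treatment as the alternative end.
3. Use the same threshold in the zero-duration rule.
4. State whether the lowest score is restricted to on-treatment visits. This matters if improvement continues after dosing stops.
5. State how the zero rule and the visit-after rule combine, and which visit counts when the lowest score occurs more than once.

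The cost is a few lines of SAP text and the matching derivation code. No new data, visits or sample size are needed.
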